10.3 CRITERIA FOR PATIENT REMOVAL FROM STUDY

Patients will be removed from study for any of the following events:

- Unacceptable toxicity (listed above in section 10.1),
- Other toxicity which investigator deems to place the patient at significant risk for toxicity
- Withdrawal of consent
- Noncompliance or inability to meet requirements of protocol
- Requirement for >4 DEB-TACE procedures
- Requirement for another anti-cancer treatment modality such as ablation, surgery, conventional TACE
- Receives a liver transplant
- Develops untreatable intrahepatic tumor progression
- Develops extrahepatic tumor progression

11.0 DEVICE INFORMATION

For further information, please refer to the product insert.

11.1 Classification

LC Bead™ is an FDA-approved permanent particulate embolic agent, which consists of a range of hydrogel microspheres that are biocompatible, hydrophilic, nonresorbable and precisely calibrated. Instructions for Use are included in Appendix 5 to the Protocol. LC Bead™ microspheres are intended to be used for the embolization of hypervascular tumors and Arteriovenous malformations. LC Bead™ microspheres carry negative ionic charge, while allows them to be ionically bound to positively-charged drug molecules, such as doxorubicin. LC Bead™ bound to doxorubicin is currently used for DEB-TACE in patients with HCC.

11.2 Mode of Action

Following injection of doxorubicin-impregnated LC Bead™ microspheres, doxorubicin is eluted from the beads over a period of 12 days. Microspheres also cause terminal tumor vessel occlusion leading to tumor hypoxia. By reducing tumor perfusion, microspheres prevent washout

of doxorubicin from the embolized tumor lesions, markedly limiting systemic concentration of doxorubicin.

11.3 Storage and Stability

Doxorubicin-loaded LC Bead™ may be stored up to 14 days at 2-8°C. After reconstitution with non-ionic contrast, doxorubicin-loaded LC Beads may be stored up to 7 days at 2-8°C.

11.4 Metabolism

Pharmacokinetic data for doxorubicin-eluting beads has already been acquired in animal models (Hong, 2006; Lewis, 2006) and in a human phase I study (Poon, 2007). Data from Hong (2006) show the pharmacokinetics of drug-eluting beads are compared with systemic or intra-arterial administration of doxorubicin in animal models and in clinical use.

11.5 Preparation

Loading instructions for 100-300µm LC Bead™ using powdered Doxorubicin 50mg vials are summarized in Appendix 6. LC Bead™ loading (steps 1-4) will be performed in a fume hood by a clinical pharmacist with experience with handling doxorubicin. Doxorubicin powder (Bedford Laboratories, Bedford, OH) will be used. National Drug Code number for the product, 50mg vials of doxorubicin powder, is 55390-233-01. Package insert for this product can be found in Appendix 7.

Step 1. Reconstitute each 50mg doxorubicin vial with 2ml of sterile water for injection. Mix well to obtain a clear red solution.

Step 2. Take flip cap off 2 100-300µm LC Bead™ vials, but do not remove metal around the bung. Remove as much saline as possible from LC Bead™ vials using a syringe and filter needle. Pierce bung with a second needle to eliminate vacuum. If a filter needle is not available, place flattened tip of needle against side of vial to prevent beads being drawn into the needle.

Step 3. Using a syringe and needle add 2 ml of doxorubicin solution directly to each vial of 100-300µm LC Bead™.

Step 4. Agitate the LC Bead™ with doxorubicin solution gently to encourage mixing and allow to stand for 60 minutes. Gently agitate the mixture occasionally during loading time.

Steps 5 and 6 will be performed by the treating interventional radiologist investigator immediately prior to and during administration of doxorubicin-loaded LC Bead™.

Step 5. Transfer the loaded beads into a 20 ml syringe using an 18-gauge needle. Expel excess liquid through an 18-gauge 5-micron filter needle.

Step 6. To prepare the loaded LC Bead™ for injection, add 10 ml of Omnipaque-350 contrast (Amersham Health, NJ) per 2 ml of LC Bead™ and mix gently using a 3ml syringe attached to the 20 ml syringe via a 3-way stop-cock. Administer suspended LC Bead™ at a rate of 1 ml per minute

11.6 Procedure

Doxorubicin-loaded LC Bead™ are administered via a co-axially placed commercially available hepatic artery catheter into hepatic arteries targeted for treatment. Procedure is performed under direct fluoroscopic visualization until near stasis of arterial flow is achieved or until a total of 4 ml of microspheres have been administered, whichever occurs first.

11.7 Incompatibilities/Contraindications

- Severe and untreatable hypersensitivity reaction to doxorubicin
- Angiographic evidence of a large hepatic artery to pulmonary vein shunt
- Angiographic evidence of a large hepatic artery to hepatic vein shunt
- Occlusion of the common hepatic duct
- Severe and refractory coagulopathy and/or thrombocytopenia
- Previous history of congestive heart failure
- Patients who are receiving P-glycoprotein inhibitors and CYP2D6 substrates that have a narrow therapeutic index for the potential risk of increased adverse events. However this risk of a drug interaction with systemically administered drugs might be low following intra-arterial bead-bound doxorubicin as compared to intravenous administration of doxorubicin.
- Because of possible hepatotoxic and nephrotoxic effect of TACE, concurrent use of hepatotoxic and nephrotoxic drugs will be avoided for a period of 2 weeks following each DEB-TACE session.

11.8 Side Effects

This section summarizes the reported complications and adverse events relating to LC Bead™ with doxorubicin used for the embolization of HCC. The literature search identified 41 articles containing safety data. A total 1584 patients have therefore been reviewed in papers reporting data on safety. (LC Bead™ 70-900 μ m).

All serious adverse events reported in these articles have been included in the table below. The overall incidence of events is calculated by taking the number of reports of each type of event and dividing by the total number of patients documented in this safety review.

Where articles specifically state the grade of event by CTCAE or other criteria, events stated to be of grade II or less have been excluded in this analysis; however the majority of reports do not state the grade of the event.

DEB-TACE has also been associated with development of liver toxicity including transaminitis, hyperbilirubinemia, synthetic hepatic dysfunction (hypoalbuminemia, coagulopathy), clinical

hepatic function decompensation (encephalopathy, ascites), gastrointestinal hemorrhage, and infections (cholangitis, liver abscess formation). DEB-TACE may lead to renal dysfunction related to development of contrast nephropathy and/or hepatorenal syndrome. DEB-TACE may cause postembolization syndrome, the symptoms of which may include pain, nausea, vomiting, fever, night sweats, fatigue, and anorexia.

Cumulative systemic levels of doxorubicin above 550mg/m² have been associated with left ventricular failure.

11.9 Availability

LC Bead™ is available in four ranges of microsphere size: 70-150 µm, (black and yellow label), 100-300µm (yellow label), 300-500µm (blue label), and 500-700 µm (red label). Drug loading with up to 75 mg of doxorubicin per 2 ml vial may be performed. Two 2 ml vials are injected during a single DEB-TACE procedure. For the purpose of this study, only 100-300µm (yellow label) LC beads will be used. Drug loading with up to 50mg of doxorubicin per 2 ml vial will be performed.

11.11 Accountability

LC Bead™ ordering and storage, doxorubicin hydrochloride ordering and storage, and microsphere loading with doxorubicin will be performed at the UCSF Inpatient Pharmacy according to LC Bead™ manufacturer-supplied loading and storage instructions.

12.0 STATISTICAL CONSIDERATIONS

12.1 Basis for Sample Size

This is an open label single arm phase II study. The primary objective is to assess the safety and to estimate the objective response rate using mRECIST in treated lesions to the DEB-TACE treatment. The response rate is assumed to be >40% in treated lesions using mRECIST on imaging approximately 1 month after last planned DEB-TACE treatment; the response rate of <20% would be unacceptable for the study treatment. If the response rate is less than a pre-specified minimum goal (i.e. 20%) then the study will be terminated due to inefficacy. Under binomial approximation with 5% type I error and 85% power, a total of 51 patients is required for the study; 17 patients will be accrued in the first stage and 34 patients will be accrued in the second stage.

12.2 Interim Analysis

After 17 patients have received at least one DEB-TACE and had potential for at least 4 weeks of follow up, the safety profile will be analyzed. The study will be terminated if one of the termination criteria based on unacceptable toxicity listed in section 10.0 has occurred. Final review of the safety will be performed within approximately three months after the treatment of the 17th patient. Stopping rules for lack of safety and efficacy after first stage are defined in Section 10.0. Accrual will continue during these interim analyses.

During the interim efficacy analysis of 17 patients, if four or fewer responses by mRECIST in treated lesions on imaging approximately 1 month after last planned DEB-TACE are observed during the first stage, the study will be stopped early; otherwise, additional 34 patients will be

accrued. If fourteen or fewer responses by mRECIST in treated lesions on imaging approximately 1 month after last planned DEB-TACE are observed by the end of the study, then no further investigation is warranted for the regimen.

Under the study design, if the response rate is <20%, the probability of ending the study during the first stage is 76%. If the response rate is >40%, the probability that the study will be stopped in the first stage is 13%.

12.3 Analysis Plan

Demographics and Baseline Characteristics

Demographic and baseline laboratory results will be summarized using descriptive statistics.

Safety Analysis

Patients will be monitored for development of recognized complications of DEB-TACE including liver dysfunction, renal dysfunction, ascites, hepatic encephalopathy, hepatorenal syndrome, biliary injury (stricture or leak), cholangitis, cholecystitis, hepatic abscess, abdominal pain, nausea, vomiting, fatigue, and fever. Adverse events will be graded according to NCI CTCAE version 4.03. Prevalence of adverse events will be summarized using descriptive statistics.

Efficacy Analyses

Analyses will be performed using the intent to treat population with exceptions as defined below, which require patient replacement.

Primary efficacy analysis

Primary efficacy will be evaluated as 1-month radiographic response after last DEB-TACE procedure in treated HCC lesions according to 1) RECIST version 1.1 and 2) mRECIST. Patients who do not have any post-baseline tumor assessments will be counted as non-responders. Point estimates of response rate and confidence intervals will be provided.

Secondary efficacy analyses

1. Overall radiographic response by 1) RECIST 1.1 and 2) mRECIST 6 months after the date of the first planned DEB-TACE procedure. This analysis will take into account all measurable hepatic HCC lesions present on cross-sectional imaging 6 months after the date of the first planned DEB-TACE procedure.
2. Time to untreatable progression (TTUP). TTUP is defined as time to disease progression untreatable by liver-directed percutaneous or surgical methods as assessed by treating investigator(s). Patient follow-up up to 1 year after last DEB-TACE will be allowed for this outcome variable.
3. Time to progression (TTP). TTP is defined as the time interval between date of first DEB-TACE procedure and date of imaging documenting development of intra- or extrahepatic disease progression by 1) RECIST 1.1 and 2) mRECIST. Patient follow-up up to 1 year after last DEB-TACE will be allowed for this outcome variable.

4. Hepatic progression-free survival (HPFS). Hepatic progression-free survival rate will be defined as the number of patients who neither progressed in the treated regions of the liver (using RECIST 1.1 and mRECIST) nor died before 1, 3, 6, 9, and 12 months after date of last DEB-TACE over the number of patients who entered the trial at these same timepoints. Estimates of the HPFS curves from the Kaplan-Meier method will be presented. Median progression event time and a 2-sided 95% confidence interval for the median will be provided using a normal approximation. For each stratum, the median, 25th and 75th percentile for HPFS will be provided.
5. Progression-free survival (PFS). Progression-free survival rate will be defined as the number of patients who neither progressed (using RECIST 1.1 and mRECIST) nor died before 1, 3, 6, 9, and 12 months after date of last DEB-TACE over the number of patients who entered the trial at these same timepoints. Estimates of the PFS curves from the Kaplan-Meier method will be presented. Median progression event time and a 2-sided 95% confidence interval for the median will be provided using a normal approximation. For each stratum, the median, 25th and 75th percentile for PFS will be provided.
6. Overall Survival (OS) is a secondary efficacy endpoint and will be analyzed 12 months after the last patient is enrolled. OS will be calculated from date of first DEB-TACE until date of death, using chart review and/or follow up phone calls to determine date of death in patients after removal from study. The survival of patients who are permanently lost to follow-up or still alive after 360 days of follow up post study discontinuation will be censored on the date the patient is last-contacted or last known to be alive. Estimates of the OS curves from the Kaplan-Meier method will be presented.
7. Proportion of patients who remain active on the waitlist and are eventually transplanted is a secondary clinical endpoint. This data will be presented using Kaplan-Meier method
8. Proportion of patients who are inactivated or drop out from the wait list for any reason but transplantation will be determined. Reasons for inactivation and/or removal from waitlist will be tabulated.
9. Proportions of patients who are successfully down-staged and achieve active waitlist status and eventually are transplanted will be determined.
10. Biochemical response defined as $\geq 50\%$ decrease in alpha-fetoprotein level measured 1 month and 4 months after DEB-TACE.
11. Histopathologic response defined as percentage of tumor necrosis at liver explant histopathology. This will only be explored in the subgroup of patients who undergo a liver transplant. Per UCSF clinical standard, tumor necrosis for HCC lesions is reported as 100%, >90%, 60-90%, 30-59%, and < 30%.

Intention To Treat Exceptions (Patient replacement)

1. Patients who proceed to liver transplant or develop hepatic decompensation between the time of enrollment and the first DEB-TACE treatment will be replaced.
2. Patients who proceed to liver transplant prior to completion of the 1 month safety window after first DEB-TACE will be replaced unless the transplant occurred due to hepatic decompensation or other toxicity attributed as at least possibly-related to protocol therapy, in which case the hepatic decompensation or other toxicity will be deemed a serious adverse event and the patient will be included in safety analysis (see Section 14.1.3).

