Secondary Objectives	
• To measure overall radiographic response (by RECIST v1.1 and mRECIST) 6 months after the date of the first planned DEB-TACE procedure.• To measure time to untreatable progression (TTUP). TTUP is defined as time to disease progression untreatable by liver-directed percutaneous or surgical methods.• To measure median time to progression (TTP)• To measure hepatic progression free survival (HPFS)• To measure progression free survival (PFS)• To measure overall survival (OS)• To determine the proportion of patients who remain active on the wait list for a liver transplant and eventually are transplanted.• To determine the proportion of patients who are inactivated or drop out from the wait list for any reason but transplantation.• To determine the proportions of patients who are successfully down-staged and achieve active waitlist status and eventually are transplanted.• To measure proportion with alpha-fetoprotein (AFP) response with $\geq 50\%$ decline from baseline (in patients with baseline level ≥ 20) post DEB-TACE and test for association with hepatic and overall response rate, PFS, and OS• To determine whether cardiac function changes occur as a result of DEB-TACE with doxorubicin• To obtain pharmacokinetic data for doxorubicin administered as a part of DEB-TACE procedures

Abstract

Study Design	Prospective open-label two-stage phase II clinical trial to evaluate the safety and efficacy of DEB-TACE in patients with liver-only HCC and significant hepatic dysfunction who are being considered for a liver transplant.
Number of patients	17 patients will be enrolled into the first stage of the study for safety and efficacy 34 patients will be enrolled into the second stage of the study
Duration of Therapy	Most patients will need only one DEB-TACE treatment, performed within 60 days of Screening procedures For patients that have more than one treatment, the procedure will be done about 4 weeks after the first, or previous treatment, up to 4 treatments total
Duration of Follow up	Post Treatment Evaluation will last 1 year
Duration of study	The study will reach completion 5 years from the time the study opens to accrual

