6.0 TREATMENT PLAN

Segmental hepatic artery catheterization will be performed via femoral artery approach using a combination of 3-French, 4-French, and 5-French angiographic catheters. Segmental DEB-TACE will be performed using two 2ml vials of LC beads (Biocompatibles, Inc.) impregnated per standard manufacturer-supplied protocol with a total of 100 mg of doxorubicin (25 mg per milliliter of beads). Microspheres in the size range of 100-300 μ m will be used. Procedure will be stopped when arterial flow approaches stasis and/or when the entire DEB dose has been administered.

Patients with multiple liver lesions, lesions >3 cm, or lesions with more than 1 feeding branch hepatic artery may receive additional DEB-TACE at approximately 1 month intervals. Cross-sectional imaging (contrast-enhanced CT or MRI) will be performed approximately 1 month after targeting of all hepatic lesions in the course of 1-4 DEB-TACE procedures. Patients with residual or recurrent disease may receive up to 4 total DEB-TACE procedures.

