Imaging Studies												
Contrast-Enhanced CT or MRI of the abdomen	X											
CT chest with and/or without contrast	X											
Cardiac Function Assessment												
Echocardiogram	X ^{&}					X ^{&}			X ^{&}			X ^{&}
DEB-TACE Procedure												
DEB-TACE**			X			X**			X**			X**
Pharmacokinetics Evaluation												
Pharmacokinetics data acquisition***			X	X	X							

Abbreviation: d = days

* See Table 2 for post-treatment evaluation after DEB-TACE 4. DEB-TACE 3 and 4 are optional for patients with disease extent limited to two liver segments. Patients may proceed to evaluation of response and long-term follow-up after fewer than 4 DEB-TACE treatments at the investigator's discretion.

& Cardiac function will be assessed via echocardiogram at baseline and one month following last planned DEB-TACE.

** Up to 4 DEB-TACE procedures may be performed at approximately 1 month intervals depending upon initial size, number, vascular supply of lesion(s) and interval treatment response on imaging.

*** See plan for pharmacokinetic data acquisition in Sections 8.1 and 8.4

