8.3 Multiple DEB-TACE Procedures Targeting Different Vascular Territories

Sequential DEB-TACE procedures may be offered in the following settings:

- A. Multifocal HCC (UNOS T2 or T3 disease; no radiographic evidence of macrovascular invasion or extracapsular extension).
- B. Single HCC greater than 3 cm (UNOS T2 or T3 disease without radiographic evidence of macrovascular invasion or extracapsular extension).
- C. More than 1 segmental feeding hepatic artery branch to a lesion of any size.

Patients with lesions that meet at least one of these criteria will be considered for up to four DEB-TACE procedures that will be performed approximately 1 month apart. Longer intervals between the procedures may be necessary in order to allow patients to regain pre-TACE liver function and performance status. Intervals between DEB-TACE procedures up to 90 days will be allowed. The timing of DEB-TACE will be determined by the treating interventional radiologist and hepatologist or medical oncologist. The number of procedures (up to 4 total) will be based on the number, location, and size of the lesions as well as on the hepatic arterial supply to the lesions. This information will be obtained from the pre-procedure cross-sectional imaging (CT or MRI) and hepatic artery angiography. This step-wise approach is intended to target the entire tumor vascular supply in a step-wise fashion prior to assessing response to therapy (Table 2).

The maximum administered doxorubicin dose per DEB-TACE procedure will be 100mg (50 mg per each 2 ml vial). The maximum administered dose as a result of four DEB-TACE procedures will be 400 mg.

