8.4.1 Patients with Single DEB-TACE Procedure

The following laboratory testing will be performed 1, 7±4, 30±7, 90±14, 180±14, 270±14, and 360±14 days following DEB-TACE: CBC, coagulation panel, BUN, creatinine, and liver function tests. Serum alpha-fetoprotein testing will start approximately 30 days following last planned DEB-TACE procedure. Any abnormal lab values will be followed up as clinically indicated. Laboratory tests may be performed at UCSF or at a local lab.

Seven ±4 days following DEB-TACE patients will have clinic follow up in Interventional Radiology for toxicity monitoring including reviewing the laboratory results above. Any expected or unexpected AEs will be discussed with the study PI or a designated co-investigator. Further testing and/or treatment will be coordinated by the study PI or a designated co-investigator if clinically appropriate (see section 7).

Cardiac function assessment monitoring using echocardiogram will be obtained approximately 30 days following the DEB-TACE procedure.

Patients will be seen in clinic approximately one month after the DEB-TACE procedure. During this visit, interim medical history will be obtained, and a physical examination will be performed. This will include (but will not be limited to) cardiopulmonary evaluation and an abdominal exam. Subsequently, patients will be followed in clinic at approximately 3 month intervals until 360 days following DEB-TACE.

Approximately one month after DEB-TACE procedure, patients will undergo repeat cross-sectional imaging with multi-phase contrast-enhanced CT or MRI of the abdomen. Subsequent imaging will be performed at approximately 3 month-intervals until 360 days following DEB-TACE. Standard clinical practices will be adhered to during the follow-up period.

Response to treatment will be assessed according to the RECIST version 1.1 and mRECIST criteria (see section 9.2).

Patients will be removed from study and follow-up assessments will stop prior to 360 days following DEB-TACE if a patient:

- a) requires > 4 DEB-TACE procedures
- b) requires another anti-cancer treatment modality such as ablation, surgery, or conventional TACE
- c) receives a liver transplant
- d) develops untreatable intrahepatic or extrahepatic disease progression
- e) experiences unacceptable toxicity (see section 10.0). All serious adverse events will be followed until the SAE has been resolved.

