9.2 Efficacy

Evaluation of the treatment response will be based on contrast-enhanced cross-sectional imaging of the abdomen (CT or MRI) performed one month following last planned DEB-TACE procedure within six months of the first DEB-TACE procedure. Treatment response will be evaluated according to both the RECIST version 1.1 and mRECIST criteria. Whenever possible, the same imaging modality (CT or MRI) will be used for pre- and post-treatment assessments.

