10.2 STOPPING RULES FOR EFFICACY

When 17 evaluable patients have been treated with at least one DEB-TACE procedure and had potential for at least 1 month of follow up, efficacy profile will be analyzed. Accrual will continue during this interim analysis period.

Stopping Rule for Efficacy after 17 patients have completed last planned DEB-TACE

1. If four (4) or fewer responses (complete, partial, or stable disease response according to mRECIST in treated lesion(s) approximately 1 month after last planned DEB-TACE) are observed among first stage of 17 patients.

During the interim efficacy analysis of 17 patients, if four or fewer complete, partial, or stable disease responses are observed in treated lesions by mRECIST on imaging approximately 1 month after last planned DEB-TACE during the first stage, the study will be stopped early; otherwise, additional 34 patients will be accrued. If fourteen or fewer responses are observed by the end of the study, then no further investigation is warranted for DEB-TACE.

Under the study design, if the response rate is <20%, the probability of ending the study during the first stage is 76%. If the response rate is >40%, the probability that the study will be stopped in the first stage is 13%.

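### Section 12.3 anchors the primary scan to the last DEB-TACE rather than the last planned one, so a session added for residual disease can move the primary read

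*Combined protocol and SAP*

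**What the plan says.** **Anchor of the primary read.** Section 12.3: "Primary efficacy will be evaluated as 1-month radiographic response after last DEB-TACE procedure in treated HCC lesions". Section 9.2 describes the response scan as "performed one month following last planned DEB-TACE procedure within six months of the first DEB-TACE procedure". The futility rule in 10.2 counts "complete, partial, or stable disease responses are observed in treated lesions by mRECIST on imaging approximately 1 month after last planned DEB-TACE". The abstract's efficacy stopping rule and sections 12.1 and 12.2 also use the last planned procedure.

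**What sets the number of sessions.** Sections 3.2 and 8.3 base it on lesion number, location and size and on arterial supply, taken from pre-procedure imaging and angiography. They intend the whole supply to be treated before response is assessed. Section 8.4.2 bases candidacy for sessions 2 to 4 on laboratory and clinical follow-up.

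**What can add sessions.** After placing the scan about a month after all lesions are targeted, section 6.0 continues: "Patients with residual or recurrent disease may receive up to 4 total DEB-TACE procedures". A Table 3 footnote makes the number of procedures vary "depending upon initial size, number, vascular supply of lesion(s) and interval treatment response on imaging". Section 8.4.1 takes a single-procedure patient off study on this ground only if the patient "requires > 4 DEB-TACE procedures". The abstract expects that "Most patients will need only one DEB-TACE treatment".

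**What is not said.** No text requires the planned number to be recorded before the response scan. No text says which scan is primary if sessions are added after it, or if a planned session is cancelled.

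**The concern.** For a patient who receives exactly the planned course, the two anchors give the same scan. They part when a session is added. The stated reason for adding one in 6.0 is residual or recurrent disease, which is what a response scan detects. Under 12.3 as worded, a scan showing non-response could lead to another session, and the scan after that session would become the primary read. Which scan is primary would then depend on what the earlier scan showed.

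The direction depends on what counts as a response. If it means complete or partial response, as the term objective response rate in 12.1 suggests, the second look goes mainly to non-responders and the shift is mostly upward. If stable disease also counts, as 10.2 says, most patients with residual enhancement already count and few remain to convert.

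Two things are at stake. The reported primary rate and its confidence interval may describe a different scan from the one the design was built on. The rate from 12.3 may also disagree with the count compared with 14 of 51.

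**Working it through.** **1. The plan's own figures.** Inputs from 10.2, 12.1 and 12.2: stop if 4 or fewer of 17 respond; negative if 14 or fewer of 51 respond; unacceptable rate 20%, target rate 40%. With X1 ~ Bin(17, p) and X2 ~ Bin(34, p):

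- P(stop early) = P(X1 ≤ 4)
- P(pass) = Σ over x = 5 to 17 of P(X1 = x) · P(X2 ≥ 15 − x)

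| True rate | Stop early | Plan states | Pass | Plan states |
|---|---|---|---|---|
| 20% | 0.758 | 76% | 0.0487 | 5% type I error |
| 40% | 0.126 | 13% | 0.854 | 85% power |

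The design reproduces. These figures assume one fixed read per patient.

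**2. Does the six-month limit in 9.2 prevent a later read?** Take a one-session plan with a scan 30 days after each session. The plan says of spacing: "Intervals between DEB-TACE procedures up to 90 days will be allowed".

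- Sessions 60 days apart: scans at days 30, 90 and 150, then 210. Two later reads fall by day 182.
- Sessions 90 days apart: scans at days 30 and 120, then 210. One later read falls by day 182.

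The limit restricts replacement but does not prevent it.

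**3. Illustration of size.** The documents give neither the number retreated for residual disease nor the number who would convert. Assume that response means complete or partial response, that the true rate is 20%, and that the 12.3 reads are used in the two-stage rule. Let m be the net number of the 51 patients converted, so the read rate is 0.20 + m/51.

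| m (assumed) | Read rate | P(pass) |
|---|---|---|
| 0 | 20.0% | 4.9% |
| 1 | 0.20 + 1/51 = 22.0% | 9.3% |
| 2 | 0.20 + 2/51 = 23.9% | 15.8% |

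Each net conversion moves the reported rate by 1/51, about 2.0 percentage points.

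**4. How often one or two patients could decide the result.** The chance of passing stage 1 and ending at 13 or 14 of 51 is 0.0363 + 0.0295 = 6.6% at a true rate of 20%, and 0.0441 + 0.0616 = 10.6% at 30%.

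**5. If stable disease counts.** At an assumed 70% disease control at month 1, P(pass) is 0.9999 on the first scan. An upward shift from a later read cannot change the decision materially; only the reported rate moves.

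**The case against.** The strongest reply is that 12.3 is shorthand. Every other place that defines the read, including both decision rules, says last planned. Sections 3.2 and 8.3 set the number of sessions from pre-procedure imaging and angiography and put treatment before assessment. Section 8.4.2 lists laboratory and clinical follow-up, not imaging, as the basis for repeat sessions, and section 3.2 checks criteria for additional treatment at a 20-day follow-up, before the 30±7-day scan window opens. A progressor would also have to meet all entry criteria again before another session. The abstract's expectation that most patients need one session may mean that few are retreated.

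Much of this stands. The plan does have a pre-procedure basis for the number of sessions, and it is an inference that the month-1 scan would trigger an added session. The inference has a textual footing, though: section 6.0 names residual or recurrent disease, and the Table 3 footnote names imaging response. Even if 12.3 is shorthand, an undated plan can be revised after the scan, so adding the word planned would not settle the matter alone.

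A second reply is that response after a full course of up to four sessions is a legitimate target. It is, but the plan would have to say so, and 12.1 ties its rate assumption to the last planned treatment.

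A reader might infer that the trial's type I error is inflated as designed. The documents do not support that: the 4/17 and 14/51 rules already use the planned anchor.

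**Conclusion.** The inconsistency is real and sits in the definition of the primary efficacy analysis. Followed literally, 12.3 allows a non-response scan to be superseded by a later one, so the reported rate and interval can shift and can differ from the count used in the stopping rules.

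The exact 4.9% type I error and 85.4% power hold as long as the rules use the planned anchor and the plan is fixed before the scan. They change only if 12.3 reads are used in the rules or the planned number is revised afterwards. The 9.3% and 15.8% figures rest on both an assumed conversion count and the complete-or-partial-response reading. They show sensitivity and are not an estimate of bias. Under the definition in 10.2, which includes stable disease, the go/no-go decision would hardly move at the assumed 70% control rate.

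This is worth correcting because the primary scan should not depend on an earlier result and the correction is cheap. It is not evidence that the design fails.

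**What to change.** 1. In 12.3, define primary efficacy as radiographic response in treated lesions *about 1 month after the last planned DEB-TACE procedure*, matching the other sections.
2. Add a short rule: the planned number of sessions is recorded by the end of the first procedure, before any post-treatment imaging; sessions added for residual or recurrent disease do not move the primary scan; if a planned session is cancelled, the scan after the last session given is used and the reason is recorded.
3. Report response after the actual last session as a sensitivity analysis, using scans already obtained.

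The cost is wording, one dated case report form field for the planned number and one reason field for a cancelled session. No extra scan is needed, and who may be retreated does not change. The downside is that the primary rate excludes any benefit from added sessions; the sensitivity analysis shows it.
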